5.5.1.1.9. Scalp Specific Investigator Global Assessment (ss-IGA)

The ss-IGA instrument is used to evaluate the disease severity of scalp psoriasis. The lesions are assessed in terms of the clinical signs of redness, thickness, and scaliness which are scored as: absence of disease (0), very mild disease (1), mild disease (2), moderate disease (3), and severe disease (4).

The analyses for ss-IGA will be based on Participants randomized at week 0 with scalp psoriasis and an ss-IGA score ≥ 2 at baseline.

5.5.1.1.10. Nail Psoriasis Area and Severity Index (NAPSI)

The NAPSI is an index used for assessing and grading the severity of nail psoriasis. Each of the participant's 20 nails (fingernails and toenails) is divided into quadrants and is assessed for any presence of nail psoriasis in the nail matrix (pitting, leukonychia, red spots in the lunula, and nail plate crumbling) and any presence of nail psoriasis in the nail bed (onycholysis, splinter hemorrhages, oil drop discoloration, and nail bed hyperkeratosis). Both the nail matrix (score 0-4) and nail bed (score 0-4) scores equal the number of quadrants affected by nail/nailbed psoriasis. The total individual nail score is the sum of the nail matrix and nail bed score and ranges from 0 to 8. The sum of all 20 individual nail scores is the total NAPSI score (0 to 160).

The analyses related to NAPSI will be based on Participants randomized at Week 0 with nail psoriasis present at Week 0.

5.5.1.1.11. Fingernail Physician's Global Assessment (f-PGA)

The f-PGA is used to evaluate the current status of a participant's fingernail psoriasis on a scale of 0 to 4 similar to the IGA (clear [0], minimal [1], mild [2], moderate [3], or severe [4]).

The analyses for f-PGA will be based on participants randomized at Week 0 with nail psoriasis and an f-PGA score greater than or equal to 2 at baseline.

5.5.1.1.12. Physician's Global Assessment of Hands and/or Feet (hf-PGA)

The severity of hand and foot psoriasis has been assessed in various clinical studies using an hf-PGA instrument. The plaques on the hands and feet are scored on a 5-point scale as: clear [0], almost clear [1], mild [2], moderate [3], and severe [4].

The analyses for hf-PGA will be based on participants randomized at Week 0 with hand and/or foot psoriasis and an hf-PGA score greater than or equal to 2 at baseline.

5.5.1.1.13. Static Physician's Global Assessment of Genitalia (s-PGA-G)

The sPGA-G is a 6-point numerical rating scale to assess the severity of genital psoriasis at a given time point. The sPGA-G evaluates erythema, plaque elevation and scale of genital psoriatic lesions. The severity of genital psoriasis is assessed as clear [0], minimal [1], mild [2], moderate [3], severe [4], and very severe [5].

The analyses for sPGA-G will be based on participants randomized at Week 0 with genital psoriasis and an sPGA of genitalia score ≥ 3 at baseline.

5.5.1.1.14. Treatment Satisfaction Questionnaire for Medications (TSQM-9 domains)

The abbreviated 9-item TSQM-9 includes 3 treatment satisfaction domains: effectiveness, convenience, and global satisfaction. Positive changes in domain scores (0 to 100) indicate improvement. The questions are ranked on a 5-point or 7-point Likert Scale ([Bharmal 2009](#)).

The calculations specific to each domain are presented in detail below:

- Effectiveness: $(\text{Item 1} + \text{Item 2} + \text{Item3}) - 3]$ divide by 18) * 100; if one item is missing, use $[(\text{sum of the two completed items}) - 2]$ divide by 12) * 100.
- Convenience: $(\text{Item 4} + \text{Item 5} + \text{Item 6}) - 3]$ divide by 18) * 100; if one item is missing, use $[(\text{sum of the 2 completed items}) - 2]$ divide by 12) * 100.
- Global satisfaction: $(\text{Item 7} + \text{Item 8} + \text{Item 9}) - 3]$ divide by 14) * 100; if item 9 is missing, use $[(\text{sum (item 7 and Item 8)}) - 2]$ divide by 8) * 100.

5.5.1.2. Analysis Methods

The efficacy data from all participants in FAS (Section [4.1](#)) will be included and analyzed by study intervention group from Week 0 through Week 16.

Similar to the secondary efficacy analyses for 77242113PSO2001 study, the endpoints will be summarized by intervention group. Simple descriptive statistics, such as n, mean, SD, median, IQ range, minimum and maximum for continuous variables and counts and percentages for discrete variables will be used to summarize most data. All statistical testing will be performed at the 2-sided 0.05 significance level. Nominal p-values will be presented. No adjustments for multiple comparisons will be made for the secondary endpoints.

5.5.1.2.1. At Week 16

The exploratory endpoints at Week 16 will be analyzed using the same main estimands and the same analysis methods described in section 5.4.1.2.2, section 5.4.1.3.1 and section 5.4.1.3.2 respectively for secondary endpoints respectively. The analysis strategy for ICEs and missing data will be handled in the same manner as the main estimand for the secondary analyses (section 5.4.1.2.2).

5.5.1.2.2. Over Time Summaries Through Week 16

In general, all endpoints with over time analyses will be descriptively summarized by treatment groups using descriptive statistics, such as mean, median, standard deviation, interquartile range, minimum and maximum for continuous variables, and counts and percentages for categorical variables.

Similar to the Week 16 analyses for the secondary continuous endpoints, MMRM model approach specified in Section 5.4.1.3.2 will be used for the over time summaries through Week 16. Least Square means (LSmeans), LS means differences and their corresponding 95% confidence interval will be provided over time through Week 16 by visit and treatment group in addition to the descriptive summary statistics.

Additionally, graphical data displays may also be used to summarize the over time data if applicable.

5.5.1.2.3. Analyses Related to PASI

- The change from baseline in PASI total score will be summarized by treatment group over time through Week 16.
- The proportions of PASI 75 responders, PASI 90 responders, and PASI 100 responders; the proportions of PASI 75 responders, PASI 90 responders, and PASI 100 responders by weight (≤ 90 kg, > 90 kg) will be summarized by treatment group over time through Week 16.
- The proportions of participants achieving $\geq 75\%$ improvement, $\geq 90\%$, or achieving 100% improvement from baseline in PASI disease component (Induration, Erythema, and Scaling) and region component (head, trunk, upper extremities, and lower extremities) will also be summarized at Week 16.

5.5.1.2.4. Analysis Related to IGA

- The proportions of participants achieving an IGA score of cleared (0); IGA score of cleared (0) or minimal (1) and the proportion of participants achieving a IGA score of mild or better (≤ 2) overall and by weight (≤ 90 kg, > 90 kg) will be summarized by treatment group over time through Week 16.

5.5.1.2.5. Analyses Related to BSA

- The change from baseline in BSA will be summarized by treatment group over time through Week 16.

5.5.1.2.6. Psoriasis Symptom and Sign Diary

The analyses for PSSD data are specified below and in general can be summarized in 3 categories as follows:

(a) Proportion of subjects who achieved clinically meaningful improvement in PSSD symptom score, sign score, and each individual scale score.

- The threshold for a clinically meaningful change from baseline in PSSD scores is defined as a change of ≥ 40 points in PSSD symptom and sign scores, change of ≥ 3 points in bleeding and stinging scores, change of ≥ 4 points in itch, dryness, cracking, skin tightness, burning and pain scores, and change of ≥ 5 points in scaling, shedding or flaking and redness scores.
- These analyses include only subjects who had at least minimal severity by each corresponding measure at baseline, i.e., a score of ≥ 40 in PSSD symptom and sign scores, ≥ 3 in bleeding and stinging scores; ≥ 4 in itch, dryness, cracking, skin tightness, burning, and pain scores, and ≥ 5 in scaling, shedding or flaking and redness scores.

(b) The proportions of subjects who achieve a score of 0 in PSSD symptom score, sign score, and each individual scale score among those who have a baseline PSSD symptom score, baseline sign score, and each individual baseline scale score that is >0 .

(c) Change from baseline in PSSD symptom score, sign score, and each individual scale score

5.5.1.2.6.1. Analyses Related to Psoriasis Symptom and Sign Diary

- The proportion of subjects with clinically meaningful improvement from baseline in PSSD symptom score, sign score, and each individual scale score at Week 16 will be compared between each of the JNJ-77242113 group and the placebo group among participants with at least minimal severity in PSSD individual scale scores at baseline, respectively.
- The proportion of subjects with clinically meaningful improvement from baseline in PSSD symptom score, sign score, and each individual scale score will be summarized through Week 16 among participants with at least minimal severity in PSSD individual scale scores at baseline, respectively by treatment group.
- The change from baseline in each PSSD individual scale score at Week 16 will be compared between each of the JNJ-77242113 groups and the placebo group.
- The proportions of participants who achieve a score of 0 in each individual PSSD scale score at Week 16 will be compared between each of the JNJ-77242113 groups and the placebo group among participants with a baseline PSSD individual scale score >0 respectively.
- The change from baseline in PSSD symptoms score, signs score, and each PSSD individual scale score will also be summarized over time through Week 16 by treatment group.
- The proportions of participants who achieve a PSSD symptoms score of 0, signs score of 0 and each individual scale score of 0 will be summarized over time through Week 16 among participants with a baseline PSSD symptoms score >0 , baseline signs score >0 , and baseline individual scale score >0 respectively by treatment group.

5.5.1.2.7. Analyses Related to DLQI

- The change from baseline in DLQI score will be summarized at Week 8 and Week 16; and the change from baseline in DLQI score at Week 16 will be compared between each of the JNJ-77242113 groups and the placebo group.
- The proportions of participants with DLQI score of 0 and 1 for the participants with baseline DLQI score >1 will be summarized at Week 8.
- The proportion of participants with a reduction of 5 or more points in DLQI score for the participants with baseline DLQI score ≥ 5 at Week 16 will be compared between each JNJ-77242113 treatment group and the placebo group and will also be summarized by treatment group at Week 8.
- The change from baseline in DLQI component scores at Week 16 will be compared between each JNJ-77242113 treatment group and the placebo group.

5.5.1.2.8. Analyses Related to PROMIS-29

- The improvement from baseline in each PROMIS-29 domain score (T-scores) will be summarized at Week 8 by treatment group.
- The proportions of participants who achieve ≥ 5 -point improvement from baseline in each PROMIS-29 domain score will be summarized at Week 8 by treatment group.
- The proportions of participants who achieve ≥ 5 -point improvement from baseline in PROMIS-29 PCS score and MCS score will be summarized at Week 8 and Week 16 by treatment group; and will be compared between each of the JNJ-77242113 treatment groups and the placebo group at Week 16.

5.5.1.2.9. Analysis Related to Genital Psoriasis Sexual Frequency Questionnaire

- The proportion of participants achieving a GenPs-SFQ item 2 score of never (0) or rarely (1) at Week 16 among those participants with a GenPs-SFQ item 2 score ≥ 2 at baseline will be compared between each of the JNJ-77242113 groups and placebo.
- The GenPs-SFQ item 2 scores will also be summarized at Week 8 and Week 16 by treatment group among those participants with a GenPs-SFQ item 2 score ≥ 2 at baseline.
- The GenPs-SFQ item 1 scores will be summarized overtime by treatment group.

5.5.1.2.10. Analysis Related to PGI-c

- The distribution of the PGI-c scale will be compared between each of the JNJ-77242113 groups and the placebo group at Week 16.
- The distribution of the PGI-c scale will be summarized at Week 8 by treatment group.

5.5.1.2.11. Analysis Related to PGI-s

- The distribution of the PGI-s scale at Week 16 will be compared between each of the JNJ-77242113 groups and the placebo group.

- The proportion of participants who achieved PGI-s of none (1), none (1) or mild (2) at Week 16 will be compared between each of the JNJ-77242113 groups and the placebo group respectively among participants with a baseline PGI-s score ≥ 3 .
- The proportion of participants who achieved PGI-s of none (1), none (1) or mild (2) and at least a 2-grade improvement at Week 16 will be compared between each of the JNJ-77242113 groups and the placebo group respectively among participants with a baseline PGI-s score ≥ 3 .
- Summary of PGI-s symptom status will be summarized at Week 8 by treatment group.

5.5.1.2.12. Analysis Related to Regional Psoriasis Disease

ss-IGA

- The proportion of participants who achieve ss-IGA score of absence of disease (0) or very mild disease (1) and at least a 2-grade improvement from baseline at Week 16 will be compared between each of the JNJ-77242113 groups and placebo group among participants with a baseline ss-IGA score ≥ 2 .
- The ss-IGA scores will also be summarized at Week 8 and Week 16 by treatment group among participants with a baseline ss-IGA score ≥ 2 and participants with a baseline ss-IGA score ≥ 3 respectively.

Nail Psoriasis Area and Severity Index

- The percent improvement from baseline in NAPSI at Week 16 will be compared between each of the JNJ-77242113 groups and placebo group for participants with a baseline NAPSI score >0 .
- The percent improvement from baseline in NAPSI will also be summarized at Week 8 by treatment group for participants with a baseline NAPSI score >0 .

Fingernail Physician's Global Assessment

- The proportions of participants who achieve an f-PGA score of clear (0) or minimal (1) at Week 16 will be compared between each of the JNJ-77242113 groups and the placebo group among participants with a baseline f-PGA score ≥ 2 .
- The proportions of participants who achieve an f-PGA score of clear (0) or minimal (1) and at least a 2-grade improvement from baseline at Week 16 will be compared between each of the JNJ-77242113 groups and the placebo group among participants with a baseline f-PGA score ≥ 2 .
- The f-PGA scores will also be summarized at Week 8 and Week 16 by treatment group among participants with a baseline f-PGA score ≥ 2 and participants with a baseline f-PGA score ≥ 3 respectively.

Physician's Global Assessment of Hands and/or Feet

- The proportions of participants who achieve hf-PGA score of clear (0) or almost clear (1) and a reduction of at least 2 grades on the hf-PGA scale from baseline at Week 16 among participants with a baseline hf-PGA score ≥ 2 will be compared between each of the JNJ-77242113 groups and placebo.

- The hf-PGA scores will also be summarized at Week 8 and Week 16 by treatment group among participants with a baseline hf-PGA score ≥ 2 and participants with a baseline hf-PGA score ≥ 3 respectively.

Static Physician's Global Assessment of Genitalia

- The proportion of participants achieving a sPGA of genitalia score of clear (0) or minimal (1) at Week 16 among participants randomized with genital psoriasis and an s-PGA of genitalia score ≥ 3 at baseline will be compared between each of the JNJ-77242113 groups and placebo.
- The proportion of participants achieving a sPGA of genitalia score of clear (0) or minimal (1) and at least a 2-grade improvement from baseline at Week 16 among participants randomized with genital psoriasis and an sPGA of genitalia score ≥ 2 at baseline will be compared between each of the JNJ-77242113 groups and placebo.
- The sPGA-G scores will also be summarized at Week 8 and Week 16 by treatment group among participants with a baseline sPGA-G score ≥ 2 and participants with a baseline sPGA-G score ≥ 3 respectively.

5.5.1.2.13. Analysis Related to Treatment Satisfaction Questionnaire for Medications

- The TSQM-9 domains will be summarized at Week 8 and Week 16; and the TSQM-9 domains at Week 16 will be compared between each of the JNJ-77242113 groups and the placebo group.

5.5.2. Study 77242113PSO2002

The objectives of the study are to evaluate long-term clinical response, patient-reported psoriasis severity, dermatology-specific health-related quality of life (HRQoL), regional psoriasis, and to explore treatment satisfaction after using JNJ 77242113 in participants with moderate to severe plaque psoriasis, the exploratory endpoints analyses will be performed.

5.5.2.1. Endpoint Definitions

The definitions of the exploratory endpoints for study 77242113OSO2002 are described in Section 5.5.1.1.

5.5.2.2. Analysis Methods

For exploratory efficacy analyses of the study 77242113PSO2002, efficacy data from the combined 77242113PSO2001 and 77242113PSO2002 studies will be included (FAS (Section 4.2)). More specifically, efficacy data will be summarized over time from Week 1 of study 77242113PSO2001 through Week 52 (Week 36 of the 77242113PSO2002 study) by treatment groups.

For overtime efficacy analyses that combines the 77242113PSO2001 and 77242113PSO2002 studies, Week 4 visit of the study 77242113PSO2002 will be aligned as Week 20 for the combined study and will be denoted as “Week 20 (LTE Week 4)” in the summary table; similar notation will be applied for the subsequent visits of the study 77242113PSO2002.

Similar to the exploratory endpoints in 77242113PSO2001, the analysis strategy for ICEs and missing data for the exploratory analyses for 77242113PSO2002 will be handled in the same manner as the main estimand for the secondary analyses of the study 77242113PSO2001 (5.4.1.2.2, section 5.4.1.3.1 and section 5.4.1.3.2).

Since 77242113PSO2002 is a LTE study following the originating study 77242113PSO2001 and no formal hypothesis testing. Simple descriptive summary statistics, such as n, mean, standard deviation (SD), median, interquartile range, minimum, and maximum for continuous variables, and counts and percentages for discrete variables will be used to summarize most data. The baseline data from the originating study (77242113PSO2001) will be used to calculate the change-from-baseline-related endpoints.

For exploratory continuous endpoints, same MMRM model approach specified in Section 5.4.1.3.2 will be used for the change from baseline at each week. Least Square means (LSmeans) and their corresponding 95% confidence interval will be provided, and no statistical testing will be performed.

Additionally, graphical data displays may also be used to summarize the over time data if applicable.

5.5.2.2.1. Analyses Related to PASI

- The proportions of PASI 75 responders, PASI 90 responders, and PASI 100 responders will be summarized by treatment group over time through Week 52.
- The change from baseline in PASI total score will be summarized by treatment group over time through Week 52.

5.5.2.2.2. Analysis Related to IGA

- The proportions of participants achieving an IGA score of cleared (0); IGA score of cleared (0) or minimal (1) and the proportion of participants achieving a IGA score of mild or better (≤ 2) will be summarized by treatment group over time through Week 52.

5.5.2.2.3. Analyses Related to BSA

- The change from baseline in BSA will be summarized by treatment group over time through Week 52.

5.5.2.2.4. Analyses Related to PSSD

- The change from baseline in PSSD symptom score, sign score, and each PSSD individual scale score will also be summarized over time through Week 52 by treatment group.
- The proportion of subjects with clinically meaningful improvement from baseline in PSSD symptom score, sign score, and each individual scale score will be summarized through Week 52 among participants with at least minimal severity in PSSD individual scale scores at baseline by treatment group.

- The proportions of participants who achieve a PSSD symptoms score of 0, signs score of 0 and each individual scale score of 0 will be summarized through Week 52 among participants with a baseline PSSD symptoms score >0 , baseline signs score >0 , and baseline each individual scale score >0 respectively by treatment group.

5.5.2.2.5. Analyses Related to DLQI

- The change from baseline in DLQI score will be summarized over time through Week 52 by treatment groups.
- The proportions of participants with DLQI score of 0 and 1 for the participants with a baseline DLQI score >1 will be summarized over time through Week 52 by treatment groups.

5.5.2.2.6. Analyses Related to PROMIS-29

- The improvement from baseline in each PROMIS-29 domain score (T-scores) and pain intensity raw score will be summarized over time through Week 52 by treatment groups.
- The proportions of participants who achieve ≥ 5 -point improvement from baseline in PROMIS-29 PCS score and MCS score will be summarized overtime through Week 52 by treatment group.

5.5.2.2.7. Analysis Related to Genital Psoriasis Sexual Frequency Questionnaire

- The GenPs-SFQ item 2 scores will be summarized over time through Week 52 by treatment group.
- The GenPs-SFQ item 1 scores will be summarized over time through Week 52 by treatment group.
- Frequency in sexual activity shift from baseline to Week 52 will be summarized over time through Week 52 by treatment groups.

5.5.2.2.8. Analysis Related to PGI-c

- The distribution of the PGI-c scale will be summarized over time through Week 52 by treatment group

5.5.2.2.9. Analysis Related to PGI-s

- Summary of PGI-s symptom status will be summarized over time through Week 52 by treatment groups.
- The distribution of the PGI-s scale will be summarized over time through Week 52 by treatment group.

5.5.2.2.10. Analysis Related to Regional Psoriasis Disease

ss-IGA

- The ss-IGA scores will also be summarized over time through Week 52 by treatment group among participants with a baseline ss-IGA score ≥ 2 and participants with a baseline ss-IGA score ≥ 3 respectively.

Nail Psoriasis Area and Severity Index

- The percent improvement from baseline in NAPSI will be summarized over time through Week 52 by treatment group for participants with a baseline NAPSI score >0 .

Fingernail Physician's Global Assessment

- The f-PGA scores will be summarized over time through Week 52 by treatment group among participants with a baseline f-PGA score ≥ 2 and participants with a baseline f-PGA score ≥ 3 respectively.

Physician's Global Assessment of Hands and/or Feet

- The hf-PGA scores will also be summarized over time through Week 52 by treatment group among participants with a baseline hf-PGA score ≥ 2 and participants with a baseline f-PGA score ≥ 3 respectively.

Static Physician's Global Assessment of Genitalia

- The sPGA of genitalia scores will be summarized over time through Week 52 by treatment group among participants randomized with genital psoriasis and an sPGA of genitalia score ≥ 2 and ≥ 3 at baseline respectively.

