To evaluate the pharmacokinetics (PK) and immunogenicity of JNJ-77242113, and explore the PK/pharmacodynamic (PD) relationship of JNJ-77242113 for biomarkers, efficacy, and safety in participants with moderate-to-severe plaque psoriasis	
 Proportion of participants who achieve at least a 5-point improvement from baseline of the originating study in each PROMIS-29 domain over time through Week 36
To characterize additional efficacy of JNJ-77242113 versus placebo for the treatment of regional psoriasis	
 JNJ-77242113 PK parameters (ie, plasma concentration just prior to the beginning or at the end of the dosing interval [C_{trough}], maximum observed plasma concentration [C_{max}], time to maximum plasma concentration [t_{max}], and area under the plasma concentration versus time curve [AUC]) The relationship between PK parameters and PD, ie, blood cellular and molecular biomarker activity as well as clinical endpoints and safety parameters The incidence of anti-drug antibodies (ADAs) to JNJ-77242113 Proportion of participants achieving a Scalp Specific Investigator Global Assessment (ss-IGA) score of absence of disease (0) or very mild disease (1) and at least a 2-grade improvement from baseline of the originating study over time through Week 36 among those participants with scalp psoriasis and an ss-IGA score ≥ 2 at baseline of the originating study Percent change from baseline of the originating study in Nail Psoriasis Area and Severity Index (NAPSI) over time through Week 36 among participants with a NAPSI score >0 at baseline of the originating study Proportion of participants achieving a Fingernail Physician's Global Assessment (f-PGA) score of clear (0) or minimal (1) over time through Week 36 among those participants with nail psoriasis and an f-PGA score ≥ 2 at baseline of the originating study Proportion of participants who achieve a Physician's Global Assessment of Hands and/or Feet (hf-PGA) score of clear (0) or almost clear (1) and a reduction of at least 2 grades on the hf-PGA scale from baseline of the originating study over time through Week 36 among those participants with hand and/or foot psoriasis and an hf-PGA score ≥ 2 at baseline of the originating study Proportion of participants achieving a Static Physician's Global Assessment (sPGA-G) of genitalia score of clear (0) or minimal (1) over time through Week 36 among participants with genital psoriasis and an sPGA-G of

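### The second of the two hand/foot (hf-PGA) subsets in the extension summaries is selected on the fingernail scale: f-PGA ≥3 is printed where hf-PGA ≥3 is evidently meant

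*SAP*

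**What the plan says.** The hand/foot bullet of SAP 5.5.2.2.10 (PSO2002) begins: "The hf-PGA scores will also be summarized over time through Week 52 by treatment group among participants with a baseline hf-PGA score". It then names two subsets: "hf-PGA score ≥ 2 and participants with a baseline f-PGA score ≥ 3 respectively". The first is defined on the hand/foot scale and the second on the fingernail scale.

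The bullet for the parent study, in SAP 5.5.1.2.12, has the same layout. It begins "The hf-PGA scores will also be summarized at Week 8 and Week 16 by treatment group among participants with a baseline hf-PGA score" of at least 2, and its second subset is "participants with a baseline hf-PGA score ≥ 3 respectively". Both cut-offs there are on hf-PGA.

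Two other places bear on the intended population. SAP 5.5.1.1.12 says that hf-PGA analyses are "based on participants randomized at Week 0 with hand and/or foot psoriasis and an hf-PGA score greater than or equal to 2 at baseline". SAP 5.5.2.1 applies the Section 5.5.1.1 definitions to the extension: "The definitions of the exploratory endpoints for study 77242113OSO2002 are described in Section 5.5.1.1" (the study number is misprinted, but PSO2002 is clearly meant).

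**The concern.** The bullet sits under the hand/foot subheading and reports hf-PGA scores, yet its second subset is picked by how bad the fingernails were at baseline. This is a selection rule that a programmer would code, not a label or background text. It would not announce itself as a mistake either. Baseline f-PGA is collected and runs from 0 to 4, as hf-PGA does, so a program written to the text would run and return a plausible table.

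At stake is the table that should show how participants with moderate or severe hand/foot disease at baseline fare through Week 52. As printed, it would show hand/foot scores in participants with moderate or severe fingernail disease.

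**Working it through.** The plan gives no figure to reproduce and no power or error rate is involved. The check is a comparison of texts, then of which participants each reading selects.

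**Step 1. Instrument used for selection in each two-subset regional bullet.**

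| Scale summarised | PSO2001 (SAP 5.5.1.2.12) | PSO2002 (SAP 5.5.2.2.10) |
|---|---|---|
| ss-IGA (scalp) | ss-IGA ≥2; ss-IGA ≥3 | ss-IGA ≥2; ss-IGA ≥3 |
| f-PGA (fingernails) | f-PGA ≥2; f-PGA ≥3 | f-PGA ≥2; f-PGA ≥3 |
| hf-PGA (hands/feet) | hf-PGA ≥2; hf-PGA ≥3 | hf-PGA ≥2; **f-PGA ≥3** |
| sPGA-G (genital) | sPGA-G ≥2; sPGA-G ≥3 | sPGA-G ≥2; sPGA-G ≥3 |

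Seven of the eight entries use the scale being summarised for both cut-offs. The hf-PGA entry for PSO2002 is the only one that changes scale. It follows directly after the f-PGA bullet, whose second subset has the same wording.

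**Step 2. Other statements of the hand/foot population.** The PSO2002 endpoint in SAP 1.1.2 is assessed "among those participants with hand and/or foot psoriasis and an hf-PGA score" of at least 2, with no f-PGA condition. SAP 5.5.1.1.12 gives the same base. Nothing in the SAP gives a reason for selecting a hand/foot display on nail severity.

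**Step 3. Who is selected.** Both scales have five grades, 0 to 4, which makes 5 × 5 = 25 possible pairs of baseline grades.

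- Intended rule, hf-PGA ≥3: 2 × 5 = 10 pairs.
- Printed rule alone, f-PGA ≥3: 5 × 2 = 10 pairs.
- Pairs selected by both rules, hf-PGA ≥3 and f-PGA ≥3: 2 × 2 = 4.
- Intended but left out, hf-PGA ≥3 with f-PGA 0 to 2: 10 − 4 = 6.
- Taken in but not intended, f-PGA ≥3 with hf-PGA 0 to 2: 10 − 4 = 6.

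If the SAP 5.5.1.1.12 base (hf-PGA ≥2) is applied as well, the printed rule selects hf-PGA 2 to 4 with f-PGA 3 or 4, which is 3 × 2 = 6 pairs. Four are intended. The other two are hf-PGA 2 with f-PGA 3 or 4. The same 6 intended pairs are still left out.

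These are counts of grade combinations, not of participants. The documents give no joint distribution of nail and hand/foot disease, so no share of participants can be stated.

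**Step 4. Comparability.** SAP 5.5.2.2 runs the extension tables from Week 1 of PSO2001 through Week 52, so they also cover Weeks 8 and 16. Under the printed rule, the ≥3 hand/foot rows at those visits would rest on a different group from the PSO2001 hf-PGA ≥3 summaries at the same visits. The hf-PGA ≥2 rows are selected by the same cut-off in both.

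**The case against.** The strongest reply is that this is a dropped letter whose intent is plain. The subheading, the first half of the bullet, the PSO2001 counterpart and the neighbouring bullets all point to hf-PGA, and the SAP has other slips of this kind, such as the misprinted study number in Section 5.5.2.1. That is a fair account of how the text arose, and nothing suggests that anyone chose f-PGA. It supports the correction rather than removing the need for it, because this slip falls inside a subset definition and would change the output if coded as printed.

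The reply also limits what can be claimed. A reader might infer that the whole extension hand/foot summary is run in the wrong participants. It is not: the hf-PGA ≥2 subset is correct, agrees with SAP 1.1.2 and 5.5.1.1.12, and still lines up with PSO2001.

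A reader might also infer that participants with clear hands and feet (hf-PGA 0) would enter and raise the share scoring 0 or 1. That follows only if the bullet is read in isolation. SAP 5.5.1.1.12, carried over by 5.5.2.1, restricts hf-PGA analyses to hand/foot psoriasis with hf-PGA ≥2, and under that restriction the only wrong entrants are at hf-PGA 2.

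Finally, one could imagine no overlap at all between the two conditions, so that none of the intended participants appear. The documents do not support that as a likely case, and it would concern only the second subset.

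**Conclusion.** The point holds for the second hf-PGA subset in SAP 5.5.2.2.10 and for nothing wider. The selection rule is wrong as printed. With or without the base population of SAP 5.5.1.1.12, it leaves out participants with hf-PGA ≥3 whose f-PGA is below 3. It also takes in participants with f-PGA ≥3 whose hf-PGA is below 3; with the base population applied, these are at hf-PGA 2 only. The ≥3 extension display would therefore not be comparable with its PSO2001 counterpart.

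The consequence is minor. SAP 2.2 makes all PSO2002 analyses descriptive, with no hypothesis. The declared hand/foot endpoint uses hf-PGA ≥2, and the ≥3 split is an additional display. No test, error rate, power statement, or primary or secondary result depends on it. The conclusion assumes that PSO2002 was meant to mirror PSO2001, which the layout of the two sections supports and nothing in the SAP contradicts.

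**What to change.** In the hand/foot bullet of SAP 5.5.2.2.10, change the second subset from a baseline f-PGA score of at least 3 to a baseline hf-PGA score of at least 3. If selection on fingernail severity was in fact intended, say so, give the reason, and label the table accordingly.

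The cost is one word in the SAP and a check that the table shell and program use baseline hf-PGA. Design, data collection and all other analyses are untouched.
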